1.0 Objectives / Specific Aims

- Purpose: Evaluate difference in postoperative opioid consumption when patients do or do not receive a quadratus lumborum block preoperatively for hip arthroscopy.
- Hypothesis: Preoperative quadratus lumborum block placement with result in decreased postoperative opioid consumption following hip arthroscopy.

2.0 Background

The number of hip arthroscopy cases has surged with over a 200% increased experienced between 2007 and 2011 [1-3]. This increased number of cases is due to both improved techniques and an increased number of indications [4-5]. As with most newer operative techniques, the optimal method of perioperative pain control is still emerging and past publications indicate that the majority of patients experience moderate to severe pain postoperative pain [6-8]. In the wake of a national opioid epidemic, consistent and reliable implementation of non-opioid analgesic strategies is exceedingly important and regional anesthesia often plays a key role in postoperative pain management.

Although quadratus lumborum blocks were first described in 2007 as an truncal block, numerous publications have recently highlighted its effectiveness as an analgesic technique for hip fracture and hip arthroplasty [9-15] and possibly the ideal regional technique for hip arthroscopy [16]. Unfortunately, prospective randomized studies are lacking. This prospective study would randomize patient to receive or not receive a quadratus plane block prior to surgery. The primary end point would be opioid consumption in the postoperative anesthesia care unit. Our hypothesis is that quadratus lumborum blocks will decrease postoperative opioid consumption.

3.0 Intervention to be studied (if applicable)

The quadratus lumborum blocks is fascial plane block. Originally described for abdominal surgery, numerous case reports and editorial publications have highlighted the effectiveness of quadratus lumborum blocks as an analgesic technique for hip fracture and hip arthroplasty [1-9] and possibly the ideal regional technique for hip arthroscopy [16]. Unfortunately, prospective randomized studies are lacking.

The anterior approach to the quadratus lumborum block is performed by injecting local anesthetic deep to the transversus abdominis aponeurosis and superficial to the fascia transversalis with direct ultrasound guidance. After completing consent, placing monitors and providing mild sedation, the patient is positioned laterally and the muscular anatomy (external oblique, internal oblique, transverse abdominis, quadratus lumborum and latissimus dorsi muscles) identified. After placing a subcutaneous skin wheal with lidocaine, a blunt regional anesthesia needle is inserted using in-plane ultrasound guidance. Local anesthetic

is deposited incrementally with frequent aspiration in the anterolateral border of the quadratus lumborum muscle at the junction of the transversalis fascia, outside the anterior layer of the thoracolumbar fascia and superficial to the fascia transversalis.

Risks of anterior approach to the quadratus lumborum block are similar to most truncal blocks and include infection, bleeding, bowel perforation or local anesthetic toxicity (LAST). Infection risk is minimized by utilizing appropriate antiseptic and sterile technique as is standard for any regional procedure. Risk of a retroperitoneal hematoma is increased with the posterior approach to the quadratus lumborum block because of its transmuscular approach and likelihood of abdominal branches of lumbar arteries in the path of the needle. For this reason, the posterior approach to the quadratus lumborum block will not be used for this study. The risk of LAST is a risk with any regional procedure and is minimized by frequent aspiration, incremental local anesthetic injection and vital signs monitoring throughout.

The quadratus lumborum block is already a block utilized daily at MUSC for a variety of surgical procedures to decrease postoperative pain. Additionally, the block has been offered at MUSC to patients with uncontrolled postoperative pain following hip arthroscopy with excellent resulting analgesia. Unfortunately, whether a patient undergoing hip arthroscopy at MUSC is offered a quadratus lumborum block for postoperative pain is currently highly provider dependent. We hypothesize that preoperative quadratus lumborum blocks will reduce opioid consumption following elective hip arthroscopy.

4.0 Study Endpoints (if applicable)

- Our primary outcome is opioid consumption including intraoperative consumption exceeding 100µg of fentanyl and all postoperative opioid consumption in the postoperative anesthesia care unit (PACU).
- Secondary outcomes include visual analog pain scaled on PACU arrival and discharge, PACU duration, patient satisfaction, block duration and opioid related side effects.

5.0 Inclusion and Exclusion Criteria/ Study Population

Inclusion Criteria

- Age greater than or equal to 18 years-old
- Undergoing elective hip arthroscopy.

Exclusion Criteria

- Local anesthetic allergy
- Chlorhexidine allergy
- Patient weight < 40kg
- Patient is currently pregnant
- Patient is unable or chooses not to give informed consent

- Emergency surgery
- Known preoperative substance abuse
- Preoperative opioid use for over three months

6.0 Number of Subjects

46

*Sample size was determined using G*Power version 3.1.9.2 software. Using preliminary data, we estimate that we will need 19 subjects in each group (N=38) to have sufficient power (80%) at alpha=0.05 to test the hypothesis of a 30% decrease in IV ME opioid consumption in patients having a QL block vs. those with no block. Accounting for a possible 20% withdrawal, we anticipate the need to enroll 46 total subjects.*

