10.0 Study Design / Methods

This prospective, single blinded clinical trial will randomize patient to receive or not receive a preoperative quadratus lumborum block prior to elective hip arthroscopy. The consent form will be distributed to patients preoperatively in the surgeon's

office. On the day of surgery in the preoperative holding area, patient undergoing elective hip arthroscopy would be informed about the trial and the block with both the risks and benefits. If they are interested in participating, informed consent would then be completed.

Once patients have signed an informed consent, they would be assigned a two-digit identification number. Numbers would be assigned sequentially with the first enrolled patient receiving "01," the second patient receiving "02," and the last patient receiving number "38." Randomization will be created prior to the study starting by a statistician with half of the research subject number being assigned to receive a nerve block and the other half assigned to not receive a block, which is our current standard of care. The regional anesthesia team will open the envelope labeled with the patient's assigned number to reveal the randomization.

Following informed consent, all patients will be positioned, prepped and sedated for a quadratus lumborum block in the preoperative holding area to blind the patient, surgeon, intraoperative anesthesia team and data collectors. The patient will be positioned in the lateral decubitus position with the operative side up and pulse oximetry and blood pressure cuff placed for monitoring. As part of routine care, the patient will receive sedation for their comfort. The relevant anatomy will then be identified using an ultrasound. The skin will be cleaned with chlorhexidine. If the subject has been randomized to the "no block" group, a subcutaneous saline skin wheel will be placed and the procedure would end at this point. If the subject has been randomized to the block group, a subcutaneous lidocaine skin wheel placed will be placed followed by a quadratus lumborum regional block with 40 ml, 0.25% ropivacaine deposited deep to the transversus abdominus aponeurosis and superficial to the fascia transversalis with direct ultrasound guidance. Local anesthetic will be injected in 5 ml aliquots with aspiration for blood performed before and after the injection of each aliquot. Local anesthetic injection will also be observed with real time ultrasound guidance.

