12.0 Data Management

Sample size and power.

Our primary hypothesis is that use of a preoperative quadratus lumborum block will decrease opioid consumption, measured in intravenous (IV) morphine equivalents (ME), by 30%.

$H_0: ME_{QL} \neq ME_{no\ block}$

$H_A: ME_{QL} < ME_{no\ block}$

The primary analysis will be a one-sided test of mean IV ME opioid consumption. Preliminary data on IV ME opioid consumption in hip arthroscopy were reviewed. In people with no preoperative block, IV ME opioid consumption averaged 18.0 ± 3.2 ; people with preoperative block averaged 9.6 ± 8.7 .

Sample size was determined using G*Power version 3.1.9.2 software. Using preliminary data, we estimate that we will need 19 subjects in each group (N=38) to have sufficient power (80%) at $\alpha=0.05$ to test the hypothesis of a 30% decrease in IV ME opioid consumption in patients having a QL block vs. those with no block. Accounting for a possible 20% withdrawal, we anticipate the need to enroll 46 total subjects.

Baseline clinical and demographic factors for each group will be collected. Categorical data will be compared across the two groups with Chi-square tests of homogeneity and continuous data will be compared with t-tests for means. Covariables determined to be associated with IV ME opioid consumption will be assessed for inclusion in a multivariate linear model.

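### Enrolling 46 covers about 17% withdrawal, not the stated 20%, if 38 analysable patients are needed; the effect on power is small

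*Combined protocol and SAP*

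**What the plan says.** Section 6.0 (Number of Subjects) gives 46 as the number of subjects. Its note says that 19 per group, 38 in total, give 80% power "at alpha=0.05 to test the hypothesis of a 30% decrease in IV ME opioid consumption", and then: "Accounting for a possible 20% withdrawal, we anticipate the need to enroll 46 total subjects". Section 12.0 (Data Management) repeats both statements. Neither section gives the inflation formula or says what the 20% is a percentage of.

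Section 12.0 also supplies the inputs to the calculation. On the test it says: "The primary analysis will be a one-sided test of mean IV ME opioid consumption". On the preliminary data it says: "In people with no preoperative block, IV ME opioid consumption averaged 18.0 ± 3.2" and "people with preoperative block averaged 9.6 ± 8.7".

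Section 10.0 (Study Design / Methods) describes sequential enrolment numbers that start at 01 and end at 38 for the last patient. The randomization list is prepared beforehand, with "half of the research subject number being assigned to receive a nerve block and the other half assigned to not receive a block".

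**The concern.** Withdrawal is normally counted as a share of the patients enrolled. On that reading, three figures printed together do not fit: 38 needed, 20% lost and 46 enrolled. The allowance is meant to protect the 38, and at the rate it names it falls just short.

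What is at stake is whether the headline enrolment figure delivers what the text says it delivers. A reader who takes the sentence at face value would believe that the 80% power survives a 20% loss. Section 10.0 adds a second mismatch on the same point, because its numbering stops at 38 and leaves no numbers for the additional patients.

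**Working it through.** **Inputs.** From Section 12.0: control mean 18.0 with ± 3.2, block group ± 8.7, a 30% decrease, a one-sided test, alpha 0.05 and power 80%. From Section 10.0: equal allocation. From Sections 6.0 and 12.0: 38 analysable, 20% withdrawal, 46 enrolled. Two assumptions are not in the documents: that ± denotes a standard deviation, and that the two SDs are pooled as a root mean square.

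**Step 1: reproduce the 19 per group.**
- Difference: 0.30 × 18.0 = 5.4.
- Pooled SD: √((3.2² + 8.7²) / 2) = √42.965 = 6.555.
- Standardised difference: 5.4 / 6.555 = 0.824.
- One-sided two-sample t-test at 0.05, noncentral t: power is 78.1% at 18 per group and 80.1% at 19 per group. The smallest number reaching 80% is therefore 19, as the plan states.
- A two-sided test would need 25 per group, so the stated figure is consistent only with the one-sided test. This agreement supports the two assumptions.

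**Step 2: the withdrawal allowance.**
- 38 × 1.2 = 45.6, rounded up to 46. This matches the plan's figure.
- 38 / (1 − 0.20) = 47.5, rounded up to 48. This is the number that leaves 38 after a 20% loss.
- 46 × 0.8 = 36.8, about 37 completers.
- 46 − 38 = 8 withdrawals can be absorbed, and 8 / 46 = 17.4%.

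**Step 3: power at 20% withdrawal** (same inputs as step 1).

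| Completers | Power |
|---|---|
| 19 + 19 (required) | 80.1% |
| 18 + 19 | 79.1% |
| 18 + 18 | 78.1% |

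If each patient withdraws independently with probability 0.20, average power is 78.6% with 46 enrolled and 80.2% with 48. Under the same model, the chance of at least 38 completers is 41% with 46 and 64% with 48.

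**Step 4: Section 10.0 beside Sections 6.0 and 12.0.** The last enrolment number is 38, and enrolment is stated as 46. As written, 46 − 38 = 8 patients would have no number and no place on the randomization list.

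**The case against.** The strongest reply is that the gap does not matter. It is 2 patients and 1 to 2 points of power, at the full withdrawal rate that the plan names. The SD behind these figures is less certain than that: raising the pooled SD from 6.555 to 6.7 takes power at 19 per group from 80.1% to 78.6%, about as much as the whole shortfall. This stands, and it is why the point is minor.

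A second reply is that the 20% may have been meant as 20% on top of 38, in which case 46 is right. The text does not rule this out, and 38 × 1.2 is itself an inference. But the sentence presents 46 as accounting for 20% withdrawal, and as a share of those enrolled 46 accounts for 17.4%. The wording needs correcting on either reading.

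A third reply is that so much loss is unlikely. Patients consent in preoperative holding on the day of surgery, and the primary outcome is complete at the end of the PACU stay. The day-one call collects only block duration and satisfaction. Withdrawal is allowed at any time, but nothing in the documents suggests that 9 or more of 46 would be lost. At 10% withdrawal, the chance that 46 enrolled give at least 38 completers is 96%; at 15% it is 75%. This also stands. It bears on the consequence and leaves the arithmetic unchanged.

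A fourth reply is that a normal approximation gives 80.3% at 18.4 per group. That is correct, but the t-test gives 79.0% there, and the plan's own requirement of 38 is missed under either method.

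A reader might infer two stronger things. One is that the trial is underpowered; power of 78–79% against a target of 80% does not support that. The other, from Section 10.0, is that only 38 patients will be enrolled. The documents do not establish this either, since Sections 6.0 and 12.0 both state 46. They show only that the sections disagree.

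**Conclusion.** Wrong as written, and minor. Whatever route led to 46, a 20% loss from it leaves fewer than the 38 that the plan requires, and nothing elsewhere in the document repairs this. That part needs only the stated figures and the usual reading of withdrawal as a share of those enrolled. The size of the power loss, 1 to 2 points, rests on the two assumptions about the SD and on a difference of 5.4. The conflict with the numbering in Section 10.0 is a separate inconsistency on the same point and should be settled together with it.

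**What to change.** In Sections 6.0 and 12.0, make one of two changes:
- state that enrolling 46 allows for about 17% withdrawal (8 of 46); or
- keep 20% and state that about 37 patients would then complete, with power of 78–79%.

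Either is a wording change and needs no extra patients. Enrolling 48 would be the matching figure if both 20% and 80% were to be kept, but the correction does not require it.

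In the same edit, reconcile Section 10.0 so that the enrolment numbers and the randomization list cover the full stated enrolment. For 46 in equal halves, that is numbers 01 to 46 with 23 per group. The cost is a short edit to three sections and, if the list was prepared only to 38, an extension of it by the statistician.

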7.0 Setting

- MUSC perioperative areas.

Study Sites

- There will not be any sites outside of MUSC.

8.0 Recruitment Methods

- Patients will be invited to participate by a study team member that is IRB approved, CITI certified and trained on the protocol. Eligibility will be determined by screening the operating room schedule for patients undergoing hip arthroscopy.
- Recruitment: Patients will be enrolled on the day of surgery in the preoperative holding area. After discussion with surgeons, patients will be educated on the role of regional anesthesia in postoperative analgesia and a quadratus lumborum block described.

9.0 Consent Process

During pre-operative appointments the surgeons will notify potential participants that they may be invited to participate in this study on the day of surgery. The surgeon will provide potential participants with the consent document to review prior to day of surgery. After discussion in the preoperative holding area regarding risks and benefits of the study and the quadratus lumborum block, patients will be consented if they choose to participate. Consent will be obtained from patient by an IRB approved CITI certified study team member that has been trained on the protocol. Copies of all documents will be provided to the patients. Once patients are consented, they will be assigned a two digit enrollment number. Prior to patient enrollment, randomization will be done by a statistician and randomized group (no block (current practice) or quadratus lumborum block) assigned based on the patient enrollment number.

10.0 Study Design / Methods

This prospective, single blinded clinical trial will randomize patient to receive or not receive a preoperative quadratus lumborum block prior to elective hip arthroscopy. The consent form will be distributed to patients preoperatively in the surgeon's

office. On the day of surgery in the preoperative holding area, patient undergoing elective hip arthroscopy would be informed about the trial and the block with both the risks and benefits. If they are interested in participating, informed consent would then be completed.

Once patients have signed an informed consent, they would be assigned a two-digit identification number. Numbers would be assigned sequentially with the first enrolled patient receiving "01," the second patient receiving "02," and the last patient receiving number "38." Randomization will be created prior to the study starting by a statistician with half of the research subject number being assigned to receive a nerve block and the other half assigned to not receive a block, which is our current standard of care. The regional anesthesia team will open the envelope labeled with the patient's assigned number to reveal the randomization.

Following informed consent, all patients will be positioned, prepped and sedated for a quadratus lumborum block in the preoperative holding area to blind the patient, surgeon, intraoperative anesthesia team and data collectors. The patient will be positioned in the lateral decubitus position with the operative side up and pulse oximetry and blood pressure cuff placed for monitoring. As part of routine care, the patient will receive sedation for their comfort. The relevant anatomy will then be identified using an ultrasound. The skin will be cleaned with chlorhexidine. If the subject has been randomized to the "no block" group, a subcutaneous saline skin wheel will be placed and the procedure would end at this point. If the subject has been randomized to the block group, a subcutaneous lidocaine skin wheel placed will be placed followed by a quadratus lumborum regional block with 40 ml, 0.25% ropivacaine deposited deep to the transversus abdominus aponeurosis and superficial to the fascia transversalis with direct ultrasound guidance. Local anesthetic will be injected in 5 ml aliquots with aspiration for blood performed before and after the injection of each aliquot. Local anesthetic injection will also be observed with real time ultrasound guidance.

Care in the perioperative period will otherwise be standardized. As part of routine care, all patients will receive general anesthesia. After receiving 100µg of fentanyl intraoperatively, hydromorphone or morphine will be administered and titrated by the anesthesia care team for postoperative pain control. In the post-anesthesia care unit (PACU), hydromorphone or morphine would continue to be titrated by the PACU nurse for the patient's comfort. The total opioids administered after the initial 100µg of fentanyl would be compared between groups in order to evaluate the effect of the quadratus lumborum block.

Data collection will begin after informed consent is completed. Data collection will include demographic data, operative date/time, medications administered intraoperative and postoperative, time to meet discharge criteria in PACU and visual analog scores (VAS) for pain and satisfaction. VAS scores for pain will be collected prior to surgery, on PACU arrival (when aware enough to do so) and upon meeting PACU discharge criteria. Patient satisfaction will be recorded upon meeting PACU discharge criteria. Effects of the block (numbness or motor weakness) will be recorded. Opioid side effects including nausea, vomiting, and itching will also be noted. Patients will be called on postoperative day one to assess block duration and satisfaction with care.

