14.0 Withdrawal of Subjects

- Subjects may withdrawal from the study at any time.

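### Section 10.0 ends the enrolment numbers, which fix the randomised group, at 38, although sections 6.0 and 12.0 plan to enrol 46

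*Combined protocol and SAP*

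**What the plan says.** Section 12.0 (Data Management, sample size and power) derives the number needed for analysis: "we will need 19 subjects in each group (N=38"), for 80% power at alpha 0.05. It then adds an allowance: "Accounting for a possible 20% withdrawal, we anticipate the need to enroll 46 total subjects". Section 6.0 (Number of Subjects) gives 46 as its entry and repeats the same reasoning.

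Section 10.0 (Study Design / Methods) describes how allocation works. After signing consent, each patient gets the next two-digit number, starting at 01, "and the last patient receiving number '38". A statistician prepares the randomisation before the study starts, with "half of the research subject number being assigned to receive a nerve block" and the rest to no block. The regional anaesthesia team opens the envelope that carries the patient's number. Section 9.0 (Consent Process) agrees that the group is "assigned based on the patient enrollment number", but gives no total.

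On losses, section 14.0 says only "Subjects may withdrawal from the study at any time". No section mentions replacing withdrawn patients, reusing their numbers, or numbers 39 to 46. The length of the list and the count of envelopes are not stated anywhere.

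**The concern.** Each enrolled patient gets one number, so the last number is the enrolment total. Section 10.0 puts that total at 38, and sections 6.0 and 12.0 put it at 46. The likeliest explanation is that the evaluable sample size was carried into 10.0 in place of the enrolment figure.

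The number is also the key to the allocation, so the discrepancy affects how the trial runs. Staff who follow 10.0 would stop at 38 and lose the whole withdrawal allowance. Staff who follow 6.0 would reach a 39th patient for whom 10.0 provides no number. If the list and envelopes were also made for 38, someone would have to extend them while the trial is running, which would put concealment and the 1:1 split at risk. That the list stops at 38 is an inference from the last patient number; the protocol does not say so.

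**Working it through.** **Can the two totals be reconciled?**

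- *Could 38 count only evaluable patients?* No. Numbers are given at consent, before surgery and before any loss is known (sections 9.0 and 10.0).
- *Could withdrawn patients be replaced within 38 numbers?* Not as written. A replacement needs a number above 38 or a rule for reusing numbers, and neither is given.
- *Does section 9.0 settle it?* No. It ties group to number without giving a total.

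**Inputs (section 12.0).** Means 18.0 ± 3.2 without block and 9.6 ± 8.7 with block; a 30% decrease; a one-sided test; alpha 0.05; power 80%; 20% withdrawal. Two assumptions are needed: the ± values are SDs, and the two SDs are pooled with equal weight. The plan states neither.

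**Reproducing the plan's 38.**

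- Difference = 0.30 × 18.0 = 5.4 mg
- Pooled SD = √((3.2² + 8.7²)/2) = √((10.24 + 75.69)/2) = 6.555
- Standardised difference d = 5.4/6.555 = 0.824
- Power = P(T > t₀.₉₅), with T noncentral t on n₁ + n₂ − 2 degrees of freedom and noncentrality d × √(n₁n₂/(n₁ + n₂))

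With 18 per group, power is 78.1%. With 19 per group, the noncentrality is 0.824 × √9.5 = 2.54 on 36 degrees of freedom, and power is 80.1%. So 19 is the smallest group size that reaches 80%, and 2 × 19 = 38 matches the plan.

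**Reproducing the plan's 46.** 38 × 1.2 = 45.6, rounded up to 46. This confirms 38 as the evaluable figure and 46 as the enrolment figure.

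**Power if enrolment stops at 38** (losses split equally between arms):

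| Lost | Per arm | Power |
|---|---|---|
| 0 | 19 | 80.1% |
| 2 | 18 | 78.1% |
| 4 | 17 | 76.0% |
| 6 | 16 | 73.6% |
| 8 | 15 | 71.1% |

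The last row is the plan's own possible 20% loss: 38 × 0.8 = 30.4, or about 15 per arm.

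**If enrolment continues to 46.** 46 − 38 = 8 patients, and 8/46 = 17.4%, fall outside the number range in 10.0. Power would be 86.6% with no loss (23 per arm) and 80.1% with 8 lost, 4 from each arm.

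**Unequal variances.** In 100,000 simulated trials with SDs of 3.2 and 8.7, power at 19 per arm was 79.9% (pooled t) and 79.1% (Welch). At 15 per arm it was 71.0% and 69.9%. The picture does not change.

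**A small related point.** A 20% loss from 46 leaves 46 × 0.8 = 36.8, so 36 or 37 evaluable, with power 78.1% to 79.1%. A true 20% allowance would need 38/0.8 = 47.5, so 48. What 46 actually covers is 8 losses, or 17%.

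**The case against.** The strongest reply is that the documents nearly settle the matter themselves. Section 6.0 is headed as the number of subjects and gives 46, and both sample-size texts explain what 38 and 46 are for. Sections 9.0 and 10.0 describe a method (a list made in advance, half the numbers to each arm, matching envelopes) that works for 46 numbers as well as for 38. On this view only one figure is wrong. That is fair as an account of the cause, and it shows the repair is easy. It does not remove the conflict: 10.0 explicitly ends the sequence at 38, and no text extends it.

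A second reply is that the harm is conditional. "Patients will be enrolled on the day of surgery in the preoperative holding area", and the primary outcome is opioid given in theatre and PACU, so losses may be few. Concealment suffers only if an extension is improvised; a concealed 46-number list made beforehand would be sound. Both points stand, and they limit the severity. Still, the plan itself allows for 20% loss.

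A third is that the power figures assume equal loss per arm. That is true: if all 8 losses from 46 fell in one arm (23 against 15), power would be 78.5% rather than 80.1%. The difference is too small to alter the conclusion.

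Last, the 17% against 20% point is separate from the numbering conflict and minor. That is also true, and it is offered only as a wording correction.

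**Conclusion.** The concern holds. The last enrolment number in 10.0 contradicts the planned enrolment in 6.0 and 12.0, and no reading of the text reconciles them. Because the number selects the envelope, this is a wrong figure that the trial relies on, and it should be fixed.

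Following 10.0 puts power below 80% as soon as patients are lost, and at about 71% under the plan's own possible 20% withdrawal. Following 6.0 leaves 8 of 46 patients (17%) outside the described numbering. The contradiction itself rests on no assumption. The powers rest on the pooled SD of 6.555, the ± values being SDs, a one-sided 0.05 test of a 5.4 mg difference and near-equal loss per arm. The risk to concealment depends on the list really ending at 38 and being extended during the trial, which the documents do not establish.

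**What to change.** - **Section 10.0:** change the last number to 46. Add that the statistician's concealed 1:1 list and the envelopes cover all of 01 to 46 (23 block, 23 no block) before the first patient is enrolled, and that a withdrawn patient's number is not reused.
- **Sections 6.0 and 12.0:** restate the allowance as up to 8 withdrawals out of 46 (17%), which is what 46 provides.

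The cost is one number, one sentence and one phrase in two places. If a list was already made for 38, the statistician regenerates it for 46, or appends a concealed set of 8 (4 per arm), before enrolment begins, and prepares 8 more envelopes. No patients are needed beyond the 46 already planned.

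### The discharge pain score is read after opioid has been titrated to comfort and says little about the block; the arrival score is usable but its timing is undefined

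*Combined protocol and SAP*

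**What the plan says.** Section 4.0 puts pain first in its list: "Secondary outcomes include visual analog pain scaled on PACU arrival and discharge". Section 10.0 adds a score before surgery and times the two postoperative ones "on PACU arrival (when aware enough to do so) and upon meeting PACU discharge criteria".

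Opioid is titrated in two stages around these readings. During surgery, after the first 100 µg of fentanyl, "hydromorphone or morphine will be administered and titrated by the anesthesia care team for postoperative pain control". In the PACU, "hydromorphone or morphine would continue to be titrated by the PACU nurse for the patient's comfort". These doses make up the primary outcome: "Our primary outcome is opioid consumption including intraoperative consumption exceeding 100µg of fentanyl and all postoperative opioid consumption", counted in the PACU.

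Section 10.0 also collects all intraoperative and postoperative medications and "time to meet discharge criteria in PACU and visual analog scores (VAS) for pain and satisfaction". The day-one contact does not add a pain score: "Patients will be called on postoperative day one to assess block duration and satisfaction with care".

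The plan does not list the PACU discharge criteria, a pain level at which titration stops, a window for the arrival score, or any rule or record on whether that score precedes the first PACU opioid. Section 12.0 describes an analysis of opioid consumption but none specific to VAS pain.

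**The concern.** Both postoperative scores are tied to events, not to the clock. The discharge score comes at the end of a process meant to make every patient comfortable. If the block works, the no-block arm should reach a similar score by using more opioid, so the effect moves out of the pain score and into the dose. If the block also shortens the time to meet discharge criteria, the arms are scored at different times after surgery, and the moment of measurement depends on treatment.

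The arrival score has a milder form of the problem. Readiness to answer after general anesthesia can plausibly depend on intraoperative opioid, which is part of the primary outcome, and a patient scored late may already have had a PACU dose.

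At stake is the reading of a listed secondary outcome. Similar discharge scores could be reported as showing that the block does not relieve pain, when titration alone could produce them.

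**Working it through.** **1. The plan's only calculation.** Section 12.0 sizes the trial on opioid consumption. Its inputs are 18.0 ± 3.2 without block, 9.6 ± 8.7 with block, a 30% decrease, one-sided α = 0.05 and 80% power.

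- Difference: 0.30 × 18.0 = 5.4
- Pooled SD: √((3.2² + 8.7²)/2) = √42.965 = 6.55
- Standardized difference: 5.4/6.55 = 0.824
- n per group: 2(1.645 + 0.842)²/0.824² = 18.2, rounded up to 19; t-test power at 19 is 80.1%

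The stated 19 per group reproduces. It does not concern VAS and is used below only as the arm size.

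**2. Order of events in section 10.0.**

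| Step | Timing | Opioid already given |
|---|---|---|
| Arrival VAS | When the patient is aware enough; no window | Intraoperative titration; PACU opioid possible, not recorded against the score |
| PACU titration | Until comfortable | – |
| Discharge VAS | On meeting criteria; varies by patient | Intraoperative and PACU titration |

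I read the discharge score in 4.0 and the score on meeting discharge criteria in 10.0 as the same reading. It follows titration by construction. The arrival score follows PACU opioid only in some patients, and the plan gives no way to tell how many.

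**3. Illustration; every VAS value is an assumption.** Untreated pain on a 0-100 scale has mean 60 without block and 40 with block, SD 25, limited to 0-100. The limits reduce the 20-point difference to about 19. A patient titrated before scoring whose pain exceeds a comfort level T is given a score spread evenly over the 15 points below T. The same share of patients is titrated in both arms. Power is two-sided at 0.05, approximately Φ(D/(s√(2/19)) − 1.96), where D is the resulting difference and s its SD. For example, with no one titrated, 19.0/(23.7 × 0.324) − 1.96 = 0.51, which gives 70%.

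| Share titrated before the score | T = 30: difference, power | T = 40 | T = 50 |
|---|---|---|---|
| 0% | 19.0, 70% | 19.0, 70% | 18.9, 69% |
| 25% | 14.7, 46% | 15.3, 53% | 16.0, 60% |
| 50% | 10.4, 29% | 11.6, 40% | 13.0, 51% |
| 100% | 2.1, 17% | 4.3, 30% | 7.2, 44% |

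The last row stands for the discharge score. With untreated differences of 15 to 25 points before limiting, the fully titrated difference runs from about 1 to 10 points. The 25% and 50% rows show what the arrival score might lose if some patients are dosed first. A higher dosed share in the no-block arm would dilute it further.

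**The case against.** The strongest reply is that the trial asks about opioid consumption. Purpose and hypothesis in section 1.0 concern nothing else, and under titration to comfort the dose is where a block effect should appear. Dose is the primary outcome and PACU duration a secondary one, so the displaced effect is captured. This stands, and it is why the point does not touch the primary result. It does not make the discharge score informative.

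A reader might infer that the pain outcome cannot show whether the block reduces pain. The documents do not support that. The arrival score is nominally taken on entry to the PACU and is compared between randomized groups, with patient and data collectors stated to be blinded. Variable wakefulness and earlier opioid would mostly dilute a difference, not remove it. A lower score in the block arm with equal or lower opioid use would still be evidence of less pain.

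A reader might also infer that a null discharge score is close to guaranteed. That would need a pain threshold in the discharge criteria or a fixed titration target, and the documents give neither. Even the fully titrated row above leaves 2 to 7 points.

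Finally, total medications and time to discharge criteria are collected, so some context for the discharge score exists. The time of the arrival score and its order relative to PACU opioid are not specified, and that gap stands.

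**Conclusion.** The point holds in a limited form. The discharge VAS is largely uninformative about a block effect, because it follows titration to comfort at a time that varies by patient and may differ by arm. A null result on it is not evidence that the block leaves pain unchanged. The arrival VAS keeps information but is weakened by its undefined time and by possible earlier PACU opioid. The bias is mainly toward no difference.

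The size cannot be computed from the documents. The figures above show the mechanism under assumed pain levels and comfort targets and are not estimates for this trial. The conclusion on the discharge score needs only that titration does what section 10.0 says it is for. The conclusion on timing needs the block to affect time to discharge criteria, which the plan treats as open by making PACU duration an outcome. This is a worthwhile, inexpensive improvement to a secondary outcome. It is no threat to the primary analysis, and the sample size does not change.

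**What to change.** Amend sections 4.0 and 10.0 on measurement only, leaving care as it is:

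- Record the clock time of the arrival VAS and whether any PACU opioid had been given before it.
- Add one VAS at an early fixed time after PACU arrival, for example 30 minutes. The documents give no PACU stay times, so the sponsor should check that nearly all patients are still there at the chosen time.
- Name the arrival and fixed-time scores as the secondary pain outcome, and state that they are interpreted jointly with opioid consumption.
- Report the discharge VAS as descriptive only, and say that similar scores do not imply absence of analgesia.

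The cost is one extra reading per patient, by staff who already collect VAS, plus the wording change. The fixed-time score is still taken during titration, so it removes the arm-dependent timing but not all of the dilution.

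Two alternatives are less suitable. A 60-minute score would be missing more often in whichever arm leaves sooner. The highest PACU score depends on length of stay and on how often patients are scored.
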